9.4 Type and Duration of Follow-up of Subjects after Adverse Events

Information on finger-prick related adverse events will be obtained from the quarterly chart abstractions.

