not possible these supervised trainings may be completed remotely via video conferencing as an option (See MOP for details and instructions). The third session will be unsupervised with the subject performing the testing in their home or temporary residence nearby the transplant center This training session will be followed up with a phone call or in-person check-in and a questionnaire to assess understanding. At each session, the subject will have written instructions on performing the DBS testing and utilizing the web/mobile technology available for their reference. Each DBS training session requires the completion of a DBS collection. The study coordinator will be available to provide additional training session as needed. In addition, DBS collection instructional video is available on the study website. Prior to discharge from the transplant care team, study personnel must confirm that the subject demonstrates proficiency in DBS sample collection and use of the study website.

The mobile technology will consist of a notification system that sends weekly reminders by email and/or text message determined by the subject's preference to the subject to complete DBS self-collection procedures. The notifications are sent from a web-based, 21 CFR 11-compliant electronic data capture system created and maintained by The Emmes Company. The subject will log into the system on a computer or mobile device with internet access to set up study reminders and record sample collection and shipment information. The system will also house IRB-approved training materials and the web address of the United States Postal Services (USPS) so that shipments may be scheduled.

Subjects who are enrolled in the control arm of the randomized study will continue to receive their office-based CMV plasma testing as recommended by standard of care.

Quarterly follow-up contacts will be made with the primary care physicians of all randomized subjects enrolled in the study to obtain each subject's medical record. Data from each subject's medical record on immunosuppression, CMV disease status, any interim use of antiviral therapy for CMV disease or plasma reactivation, clinically recommended CMV test interval, any hospitalization record, relapse, and survival status will be collected.

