7.5 Follow-up (Quarterly, ± 2 weeks)

Quarterly follow-up contacts will be done on all randomized subjects while enrolled in the study regardless of the randomization status. Study sites will follow up with subjects' primary care physicians to obtain the following records at each quarterly time point based on transplant date:

- Current immunosuppression
- Systemic steroid use
- Recommended CMV test interval (i.e., testing frequency)
- Office-based CMV test dates and results (i.e. PCR, IHC, histopathology, etc.)
- Interim hospitalizations
- CMV disease status
- Interim use of preemptive therapy for late CMV disease
- AEs
- Date of morphological relapse
- Survival status
- Problems with DBS or plasma kit integrity

If the scheduled quarterly visit is within 10 days of subject randomization, the corresponding quarterly visit will be waived.

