7.6 Final Study Visit

At approximately 12 months after HCT (+4 months), study staff will conduct a closeout data collection of both randomized and observational cohorts by obtaining subject's medical records. The following information should be recorded on the appropriate electronic case report form:

- Current immunosuppression
- Systemic steroid use
- Recommended CMV test interval (i.e., testing frequency)
- Office-based CMV test dates and results (i.e. PCR, IHC, histopathology, etc.)
- Interim hospitalizations
- CMV disease status
- Interim use of preemptive therapy for late CMV disease

DMID/NIAID/NIH CONFIDENTIAL

- AEs
- Date of morphological relapse
- Survival status
- Problems with DBS or plasma kit integrity

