9 ASSESSMENT OF SAFETY

9.1 Adverse Events

AEs will be elicited from subjects in the DBS arm at quarterly follow-up contacts and at the final closeout contact.

For this trial, a reportable AE is defined as any clinically important untoward medical experience directly related to DBS collection, that is, the finger-stick procedure. The study source documents will include the assessment and evaluations of all AEs as defined above.

Only those events that are considered "Severe" and "Related" to the DBS collection and finger stick procedure will be reported. See below for definition of "Severe" and "Related":

- Severe: Events interrupt a subject's usual daily activity and require systemic drug therapy or other medically administered treatment.
- Related: There is a reasonable possibility that the study product caused the adverse event. Reasonable possibility means that there is evidence to suggest a causal relationship between the study product and the adverse event.

AEs as defined above are reported on appropriate CRFs in the AdvantageEDCSM.

If an AE is considered "Unexpected", the appropriate CRF must be submitted within 10 calendar days.

 Unexpected: Event is not listed in study materials or is not listed at the specificity or severity that has been observed; or is not consistent with the risk information described in the general investigational plan. For example, under this definition, an infection requiring antibiotic treatment and causing a missed day of work may be considered Expected. An infection causing an extended absence from work or leading to necrosis may be considered Unexpected.

DMID Medical Monitor will review adverse events and determine if additional reporting is applicable.

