4.5.2. Secondary Outcome Measures

• The total number of recommended clinician recommended CMV monitoring tests that were completed per participant in the study period by 1 year after HCT will be defined as in Section 3.3.

The primary and secondary adherence outcomes will be analyzed with ITT, mITT and completer populations during the Study Period defined in Section 3.3.2. A sensitivity analysis will be conducted to exclude all participants from the University of Minnesota for the primary and secondary adherence measures.

In addition, sensitivity analyses with Maximal Study Period defined in Section 3.3.3 will be performed with ITT, mITT and completer populations with and without the participants from the University of Minnesota.

- The number of participants in the DBS and standard of care arms with possible, probable or proven end-organ CMV disease in the study period by 1 year after HCT will be measured from data entered by clinic staff during medical chart abstraction. Chart abstraction will occur at enrollment, quarterly contacts and at the study close-out visit. Proven/probably breakthrough CMV disease will be considered as a Serious Adverse Event of Special Interest (SAESI).
- Finger-stick procedure-related Grade 3 AEs will be abstracted through medical chart review at quarterly contacts and at the final close-out contact as described in the Manual of Procedures (MOP). Participants will be considered as meeting the outcome measure if they have at least one finger-stick procedure-related Grade 3 AE during the study period.

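### Protocol 9.1 promises to elicit finger-stick adverse events from subjects, but the operative sections and the SAP take them from charts, so qualifying events may be missed

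*Protocol*

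**What the plan says.** The documents give two accounts of where finger-stick AE data come from.

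- **The subject.** Protocol 9.1: "AEs will be elicited from subjects in the DBS arm at quarterly follow-up contacts and at the final closeout contact". The SAP 9.2.1 heading and the SAP Table 4 title also call these events elicited.
- **The chart.** Protocol 9.4: "Information on finger-prick related adverse events will be obtained from the quarterly chart abstractions". SAP 4.5.2, for the secondary safety outcome: "Finger-stick procedure-related Grade 3 AEs will be abstracted through medical chart review at quarterly contacts and at the final close-out contact", with the detail left to the Manual of Procedures (MOP).

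The sections that describe the contacts agree with the second account. Protocol 4.1: "Quarterly follow-up contacts will be made with the primary care physicians of all randomized subjects enrolled in the study". Protocol 7.5 has sites approach "primary care physicians to obtain the following records at each quarterly time point based on transplant date", and AEs are on that list of records. At closeout, Protocol 7.6 says "study staff will conduct a closeout data collection of both randomized and observational cohorts by obtaining subject's medical records", again with AEs on the list.

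A reportable AE under Protocol 9.1 must be both Severe and Related. Severe requires interruption of usual activity and also systemic drug therapy or other medically administered treatment. SAP 9.2.1 and Table 24 report the proportion of DBS-arm participants with such an event, with an exact 95% binomial interval.

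**The concern.** A site can follow Protocol 7.5, 7.6 and 9.4 to the letter and never ask a subject about the finger stick, although 9.1 says subjects will be asked. Finger-stick AEs are the whole of secondary outcome 3. For a chart to yield one, it has to show the treatment and also allow a link to the lancet. Treatment by a provider whose notes are not abstracted would not reach the count, nor would a charted finger infection with no mention of the study.

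The planned interval expresses sampling error only. If capture is incomplete, a count of zero or nearly zero looks more reassuring than it is, and a heading that calls the events elicited would tell readers that subjects had been asked. Dependence on record requests can also delay the site's awareness of an Unexpected AE, which Protocol 9.1 wants submitted within 10 calendar days.

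**Working it through.** **1. Is there any other place where the subject is asked?**

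- Quarterly contacts (Protocol 4.1, 7.5): with the primary care physician, for records.
- Closeout (Protocol 7.6): medical records.
- Schedule of events (Protocol Appendix C): has a safety-monitoring row at the quarterly and final columns, but does not say who is asked.
- Subject questionnaires (Protocol 7.4.1): described as covering training, reminders and shipping. The items shown in SAP Table 33 include no finger-stick harm item. SAP Table 34 is partly a placeholder, so the end-of-study form cannot be fully checked.
- Contact by design: Protocol section 5 keeps direct contact as equal as possible between arms, and SAP 4.4.8 limits contact during the study period.
- Kit problems (Protocol 10.1; Appendix C, footnote 11): subjects report kit failures, and an AE form follows if AE criteria are met.
- Unanticipated Problems (Protocol 9.3): investigators report these whatever their severity.

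The last two are real routes from subject or investigator to the database. Neither asks every DBS subject about harm.

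**2. What could incomplete capture do to the reported rate?**

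The documents give no expected AE rate, capture rate or precision target, so there is no stated figure to reproduce. What follows is an illustration.

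Inputs: n = 100 in the DBS arm (Protocol 5.3.1); exact binomial 95% interval (SAP 9.2.1); capture fraction s, the assumed probability that a subject with a qualifying event is recorded.

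For 0 of n recorded, the two-sided exact upper limit is U = 1 − 0.025^(1/n) = 1 − 0.025^(1/100) = 3.62%. The recorded rate is the true rate p times s, so the limit on p is U/s:

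| Assumed s | Upper limit on true rate |
|---|---|
| 100% | 3.6% |
| 75% | 3.62/0.75 = 4.8% |
| 50% | 3.62/0.50 = 7.2% |
| 25% | 3.62/0.25 = 14.5% |

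The chance of recording no event at all is (1 − p·s)^100. With an assumed true rate of 2%:

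- s = 100%: 0.98^100 = 13%
- s = 50%: 0.99^100 = 37%
- s = 25%: 0.995^100 = 61%

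**3. How long can an event wait?**

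Protocol Appendix C puts Contact 3 at day 270 and the final visit at day 365 with a window of +120 days. The longest planned gap between record requests, counted from the Contact 3 target date, is 365 + 120 − 270 = 215 days. Protocol 9.1 does not say from when its 10 days run. If they run from site awareness, the gap delays the start of the clock rather than breaching the limit.

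**The case against.** The case on the other side has several parts.

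- **Charts are not the only route.** A reader might infer that harm is taken only from primary-care charts. The documents do not support that. Protocol 9.4 and SAP 4.5.2 do not limit the type of chart, closeout uses medical records generally, and the kit-problem and Unanticipated Problem routes exist. This stands, and it narrows the point to a lack of systematic questioning.
- **Most harm at home is outside the outcome anyway.** A reader might infer that harm at home goes uncounted. Untreated pain, bruising or minor infection is excluded by the Severe definition, whatever the data source. Qualifying events involve treatment and would usually leave some record. This also stands. What remains is treated events that are recorded elsewhere or not linked to the finger stick.
- **Protocol 9.4 may concern only follow-up after an AE,** as its heading suggests, so that sites still elicit under 9.1. That reading is possible, but it leaves the conflict between 9.1 and SAP 4.5.2 in place, and also the fact that the contacts named in 9.1 are described elsewhere as record requests.
- **The MOP may describe the process.** It was not available for this review. It could add a procedure, but would not make the protocol and SAP agree.
- **Limited contact is deliberate.** Extra staff contact in one arm could disturb the adherence comparison. This is a fair constraint on the remedy, and it argues for a web item rather than calls.

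**Conclusion.** The contradiction is in the text and needs no assumption: Protocol 9.1 names the subject as the source, while Protocol 9.4, the contact procedures in 4.1, 7.5 and 7.6, and SAP 4.5.2 name records. The consequence is that qualifying events absent from the abstracted record, or not attributable from it, may be missed, and the interval for secondary outcome 3 does not show this.

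How many would be missed cannot be worked out from the documents. The range of 4.8% to 14.5%, against 3.6% at full capture, rests on assumed capture of 75% to 25%, the planned 100 DBS subjects and a zero count. No single value in that range should be quoted as an estimate. Nor do the documents show that a low observed rate would be caused by poor capture, only that the plan could not tell the two apart. The possible interval of about 215 days between the last two record requests follows directly from the schedule.

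This is worth correcting because the remedy is cheap and the outcome is a stated safety objective. The primary adherence analysis and its power are unaffected.

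**What to change.** 1. **Reconcile the text.** Make Protocol 9.1, 9.4, 7.5, 7.6 and SAP 4.5.2 name one source: subject report plus chart review. Cost: wording changes.
2. **While follow-up continues, ask the subject.** Add one yes/no item, on whether the finger stick needed medical treatment or interrupted usual activity, to the web shipment form that subjects already complete, or to the 1-month and end-of-study questionnaires. Site staff follow up only on a yes. The shipment form gives earlier notice. The end-of-study questionnaire can also reach a subject who has stopped collecting and no longer opens that form. Cost: one field on an existing electronic form and IRB notification, with no added visit or scheduled staff contact. The downside is small: some minor reports will need triage against the Severe and Related definitions, and a yes brings a contact in the DBS arm only.
3. **For subjects already finished, label the data as they are.** Replace *Elicited* with *chart-abstracted* in the SAP 9.2.1 heading and the Table 4 title. Table 24 does not carry the word, so it needs only a footnote naming the source. State possible under-capture as a limitation of the reported rate and its interval.

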9.5 Safety Oversight

9.5.1 Data and Safety Monitoring Board (DSMB)

The DMID DSMB is convened by authority of DMID and is advisory to DMID and the study team. The DMID DSMB must consist of at least three voting members including a biostatistician experienced in statistical methods for clinical trials and a clinician with relevant expertise. Selection of DMID DSMB members should include consideration of clinical trials experience, relevant expertise, prior DSMB service, and absence of significant conflict of interest. DMID is responsible for deciding whether consultancies or the financial interests of the members materially affect their objectivity. Members will notify DMID promptly if a change occurs that may create a potential conflict of interest.

The DMID DSMB will operate under the rules of a DMID-approved charter that will be reviewed and finalized following the organizational meeting of the DSMB. The DMID DSMB Charter serves as the standard operating procedure and defines the primary responsibilities of the DSMB, its membership, the purpose and timing of its meetings, data to be reviewed, and procedures for ensuring confidentiality and proper communication. The following times are the proposed scheduled meetings of the DMID DSMB:

- Organizational DMID DSMB meeting –The first meeting of the DMID DSMB will be primarily organizational and to review the study protocol, safety data shells, and frequency of scheduled meetings. This meeting will occur prior to the initiation of study enrollment.
- Interim analysis data review meeting- Among the first 50 subjects enrolled on the DBS intervention arm and followed for at least a year, if the lower one-sided 90% confidence interval for the percent of subjects experiencing CMV disease by one-year exceeds 8% (operationally 7 out of 50), a DSMB meeting will be convened. The DSMB will be charged with determining whether this exceptionally high rate of CMV disease has plausible clinical explanations related to the subject characteristics, or if it is the result of a failure in the monitoring system, and if so, what the source of the failure is (lack of compliance, failure of the system). Ultimately, they will make a recommendation to the PI as to whether any aspect of the study should be modified or terminated.
- Ad Hoc meeting to review safety events such Unanticipated Problems or SAESIs (breakthrough CMV disease reports).
- Final DMID DSMB meeting 6 to 8 months after clinical database lock to review the cumulative safety data for the study. The data will be provided in a standard summary format. The DSMB may be asked to provide recommendations in response to questions posed by DMID.

The DMID DSMB may also be convened for an *ad hoc* meeting, an unplanned meeting that is called for a specific purpose such as when a study halting rule is met. The meeting can be requested by any party with the responsibility of overseeing the trial (such as the PI, DSMB, DMID). In the case of an *ad hoc* meeting, the DMID DSMB may request special reports on an as-needed basis.

If the study is discontinued, follow-up visits for safety would continue.

10 MONITORING

10.1 Study Kit Monitoring

The clinical sites are responsible for verifying the integrity of the study kit before supplying subjects with kits at enrollment and resupplies. Both the DBS and Confirmatory Whole Blood kits will be verified. The subject will be instructed to report problems with study kit integrity to the clinical site. If a problem is identified with study kit, the subject will contact the site, which will record problems on the appropriate eCRF. The subjects will submit resupply requests of additional study kit through the web/mobile technology.

The SDCC will perform data logic checks and queries on the data entered into the data collection system.

11 STATISTICAL CONSIDERATIONS

11.1 Study Outcome Measures

11.1.1 Primary Endpoint

The primary endpoint will be the proportion of subjects who complete >90% of their recommended CMV monitoring tests by 1-year post-transplant. We will use logistic regression modeling to compare this proportion between subjects randomized to DBS testing versus standard office-based testing. Since randomization will be stratified by transplant site and subject's perceived ease of access to blood draw facility, these factors will be used as adjustment factors in the models.

For each subject, the number of CMV monitoring tests performed will be assessed and the percent of recommended tests will be calculated. Subjects with percent completion >90% will be considered a success with regard to the primary endpoint. The personspecific denominator for the proportion, number of expected CMV monitoring tests, will be variable and dependent on subjects' immunosuppression and hospitalizations during the study. For example, subjects in this study that are highly immunosuppressed a weekly monitoring schedule is generally recommended, often throughout the first year after transplantation. If such a subject were discharged from the primary transplant center at day 100, there would be 38 remaining tests until day 365 after HCT (if the subject is still alive at 1 year). We will assess the actual number of tests performed and calculate the percent of tests (e.g. 36/38 = 94.7%). Another scenario would be for a subject that stopped monitoring and was then re-started on high-dose steroids for treatment of GVHD with resumption of weekly testing, resulting in yet another denominator. Study participants in the DBS arm who are hospitalized during the study should not collect DBS samples while admitted. Rather, admitting hospitals should monitor participants for CMV with plasma CMV DNA PCR testing as recommended for their level of immunosuppression. Those inpatient testing timepoints will not be included in the person-specific denominator.

The primary analysis will be an intent-to-treat (ITT) analysis of all subjects randomized. Another key analysis will be the modified intent to treat analysis of all subjects who had at least one test done after discharge from the primary transplant team.

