7.3 Weekly DBS Testing

Subjects randomized to the DBS arm are instructed to collect DBS on the same day and at approximately the same time each week (Sunday through Wednesday to avoid delays due to weekend shipping) following the provided instructions (refer to MOP). Subjects will start weekly

DMID/NIAID/NIH CONFIDENTIAL DBS collections the week after discharge and continue until approximately 1 year after HCT even following a positive result or initiation of preemptive therapy. If a DBS participant is hospitalized, the participant should not collect weekly DBS samples during hospitalization. The admitting hospital should monitor the DBS participant for CMV with at least weekly plasma CMV DNA PCR testing during hospitalization. Once discharged, the study team will remind the participants to resume DBS collections according to their weekly schedules. The study team may provide a refresher DBS training if needed. If a subject's DBS result is positive, and/or prior to any initiation of standard-of-care preemptive therapy, a 6ml whole blood (EDTA anticoagulant tube) will be collected for plasma CMV PCR analysis by the subject's physician or referred collection site and an additional DBS sample at their scheduled laboratory visit with exemption to emergent hospital visit or hospitalization. Subjects will be provided with a pre-paid mailer with instructions to deliver to the collection center to assist with plasma CMV sample shipment to University of Washington Clinical Virology Laboratory on the day of collection. The subject will need to collect a DBS test at the time of the plasma collection. Subjects will be provided with a DBS kit to take with them to the physician's office. USPS should be contacted from the physician's office for pickup of the completed DBS kit.

All test results will be transmitted via a secure server to the study sites from the laboratory. The research staff will then contact the subjects' treating physicians via phone/fax. The subjects will receive a notification via the study web portal when their positive CMV test results are available with a link to a secure website that can be used to access them.

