3.3.2. Study Period

The study period for all safety analyses is defined as the time from enrollment to End of Follow-up.

The study period for all adherence analyses and DBS collection compliance analyses is the time from discharge to End of Follow-up. For participants in the DBS arm who were hospitalized during the follow-up, the duration of hospitalization will be subtracted from the study period for assessment of compliance with DBS collection.

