APPENDIX 4. WORKED EXAMPLES OF NUMBER OF EXPECTED TESTS

For a given participant, the number of expected tests is derived based on the start dates of the intervals as follows:

Notation:

- 1. Let $t_{i,0}$ denote the date of discharge for participant *i*
- 2. Let $c_i \in \{0, 1, ...\}$ denote the number of times participant *i*'s recommended monitoring interval was changed by their primary care physician during the study period, defined for each participant as the time from enrollment to the earlier of Protocol Completion and Early Termination.
- 3. Let $t_{i,1}, ..., t_{i,c_i}$ denote the times at which the recommended monitoring interval was changed for participant *i*. $t_{i,1}$ is the end date of the initial interval for participant *i*.
- 4. Let t_{i,c_i+1} denote the end of the monitoring period for participant *i*. This is the earlier of the end of the study period or the date after which recommended monitoring is no longer required.
- 5. Let $d_{i,1}, ..., d_{i,c_i}$ denote the corresponding number of days between recommended monitoring tests when the recommended frequency is changed at times $t_{i,1}, ..., t_{i,c_i}$. The days $d_{i,j}$ take the value 7 if recommended frequency is weekly, 14 if the frequency is bi-weekly, 30 if the frequency is monthly and 90 if the frequency is quarterly, 3.5 if the frequency is twice a week, and 17.5 if the frequency is every 2-3 weeks. The initial recommended monitoring frequency should be weekly so the number of days between tests, $d_{i,o}$, should be 7.
- 6. Let $I_{i,j}$ denote the recommended monitoring interval for the j^{th} change to the recommended frequency for participant *i*. The recommended monitoring interval(s) for participant *i* are therefore

$$I_{i,0} = [t_{i,0}, t_{i,1}], I_{i,1} = (t_{i,1}, t_{i,2}], \dots, I_{i,c_i} = (t_{i,c_i}, t_{i,c_i+1}]$$

The number of expected tests in the first interval is calculated as follows. It is assumed that the first expected test is $d_{i,0}$ days after $t_{i,0}$. Let $n_{i,0}$ denote the number of expected tests during $I_{i,0}$. Then,

$$n_{i,0} = floor\left(\frac{t_{i,1}-t_{i,0}+1}{d_{i,0}}\right).$$

Let $m_{i,0}$ denote the date of the last expected recommended monitoring test for participant *i* during interval I_{i0} . Then,

 $m_{i,0} = t_{i,0} + d_{i,0} n_{i,0}.$

There are two possibilities for changes in the monitoring frequency:

1. Frequency in interval $I_{i,j}$ is less frequent than in $I_{i,j-1}$, i.e. $d_{i,j} > d_{i,j-1}$

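### The protocol takes inpatient weeks out of the primary denominator, the SAP's primary denominator does not, and neither document gives one hospitalization rule for both arms

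*Protocol*

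**What the plan says.** Protocol 11.1.1 calls a participant a success as follows: "Subjects with percent completion >90% will be considered a success with regard to the primary endpoint". It says the person-specific denominator varies with "immunosuppression and hospitalizations during the study", naming no arm. The operative sentences come later and name one arm: "Study participants in the DBS arm who are hospitalized during the study should not collect DBS samples while admitted". The admitting hospital is to test instead, and then: "Those inpatient testing timepoints will not be included in the person-specific denominator". No matching sentence covers SOC participants.

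SAP 3.3.2 defines the period for adherence analyses and for DBS-collection compliance as discharge to end of follow-up. For the DBS arm it adds that "the duration of hospitalization will be subtracted from the study period for assessment of compliance with DBS collection". Adherence analyses are not mentioned in that sentence.

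The primary denominator is built in SAP 3.3.4 and Appendix 4, where "the number of expected tests is derived based on the start dates of the intervals as follows". The formulas use discharge, schedule-change and end dates. Neither they nor the three worked examples have a hospital term. SAP 3.3.5 takes the numerator as the chart-review records up to end of follow-up, without saying whether tests done in hospital count. SAP section 17 lists only the analysis without University of Minnesota participants as a change.

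**The concern.** Two programmers working from these documents could build different primary endpoints. One could remove inpatient weeks in the DBS arm (Protocol 11.1.1 taken literally, or SAP 3.3.2 applied through the cross-reference in 3.3.4). The other could remove none (Appendix 4 as written). The choice matters because the >90% cut-off is tight: a few weeks in hospital can decide success or failure whatever the participant does as an outpatient.

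Two harms are possible. If weeks are kept and inpatient tests are not recorded, hospitalized participants fail for reasons unrelated to adherence, and the trial loses power. If weeks are removed in one arm only, the arms can differ with no difference in adherence. The trial is unblinded, so the rule should be fixed before anyone sees which version helps which arm.

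**Working it through.** **1. The plan's own figures.** Protocol 11.1.1 says that for weekly testing after discharge at day 100 "there would be 38 remaining tests until day 365 after HCT". The Appendix 4 formula agrees: floor((365 − 100 + 1)/7) = floor(266/7) = 38. The stated power also reproduces. With 50 SOC and 100 DBS, 0.50 v 0.80, two-sided 0.05 and pooled variance: the pooled rate is 0.70, the null SE is √(0.70 × 0.30 × (1/50 + 1/100)) = 0.0794, and the alternative SE is √(0.25/50 + 0.16/100) = 0.0812. Then (0.30 − 1.96 × 0.0794)/0.0812 = 1.78, a power of 0.96. For controls of 0.55 and 0.58 the same formula gives 0.885 and 0.80, against 89% and 80% in the plan.

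**2. How tight the cut-off is.** With 38 expected tests, >90% means more than 34.2, so 35 are needed and 3 may be missed.

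**3. One participant, three answers.** 38 expected tests, a 3-week admission, 32 of 35 outpatient tests done:

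| Rule | Score | Result |
|---|---|---|
| Weeks removed, inpatient tests not counted | 32/35 = 91.4% | success |
| Weeks kept, no inpatient test recorded | 32/38 = 84.2% | fail |
| Weeks kept, all three recorded | 35/38 = 92.1% | success |

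With four inpatient weeks kept and no test recorded, even perfect outpatient adherence gives 34/38 = 89.5%, a fail.

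**4. Size across a trial.** The documents give no hospitalization rate, length of stay or capture rate, so these are assumed: a share h hospitalized, for w weeks, with a test recorded in a share r of those weeks. Weekly completion is binomial, set to about 0.90 so that a participant with 38 expected tests and no admission succeeds 50% of the time, in both arms.

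*DBS-only exclusion, equal adherence, h = 20%, w = 4.* With weeks removed, a hospitalized participant has 34 expected tests and may still miss 3, so success is 58.7%. The DBS arm is 0.8 × 50% + 0.2 × 58.7% = 51.7%. The SOC arm keeps the weeks:

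| r | SOC success | Spurious difference | Chance of a significant result |
|---|---|---|---|
| 0 | 0.8 × 50% + 0.2 × 0% = 40.0% | 11.7 points | 0.29 |
| 0.5 | 43.8% | 7.9 points | 0.16 |
| 1 | 51.7% | 0 | 0.056 |

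The last figure is this test's level with no hospitalization at all. Over h = 10–40% and w = 2–4 at r = 0, the difference runs from 4 to 24 points. Allowing correlation of 0.3 between a participant's weeks, it runs from 1 to 21.

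*Nothing removed in either arm (SAP as naturally read), 0.80 v 0.50, h = 20%, w = 4.* At r = 0 the rates become 0.8 × 0.80 = 0.64 and 0.8 × 0.50 = 0.40, and power falls from 0.96 to 0.80. At r = 0.5 it is 0.92, and at r = 1 it is 0.96.

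*Weeks removed but inpatient tests still counted.* A hospitalized participant with a test every inpatient week goes from 50% to 88% (w = 2) or 99% (w = 4). The numerator and denominator must therefore follow the same rule.

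**5. Same rule in both arms, weeks and tests both removed.** Equal adherence gives no arm difference, and power for 0.80 v 0.50 stays at 0.95–0.96 for h = 10–40% and w = 2–4.

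**The case against.** A reader might infer that the plan as it stands tilts the primary comparison toward DBS by about 10 points. The documents do not support that, for four reasons.

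- Protocol 11.1.1 makes the denominator depend on hospitalizations for subjects in general. The DBS sentences may be there only because that arm has self-collection to suspend. Protocol 7.2.2 says SOC activities otherwise match the DBS arm. The SOC rule is unstated, which is not the same as a rule to keep SOC weeks.
- The SAP's primary endpoint counts chart-review tests ordered by the clinical team in both arms (3.3.5, 4.4.1). Keeping all weeks and counting recorded tests is coherent and arm-neutral. The DBS-only subtraction has a natural home in DBS-collection compliance, which exists in one arm only.
- Protocol 7.3 says "The admitting hospital should monitor the DBS participant for CMV with at least weekly plasma CMV DNA PCR testing during hospitalization". If those tests are done and recorded, keeping and removing weeks agree: at 38 expected tests, 3 misses are allowed under either rule for stays of up to 7 weeks.
- The admission rates behind any 10-point figure are assumed.

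All four points stand as limits on size and direction. They do not reconcile the documents. SAP 3.3.5 does not say that inpatient tests count, and Protocol 7.5 and 7.6 describe the abstracted tests as office-based. The explicit instruction for inpatient plasma testing in 7.3 and 7.7 names DBS participants, although the hospital letter in 7.7 goes to all study subjects. Complete and equal capture is therefore not assured. Because 3.3.4 takes its study period from 3.3.2, a DBS-only subtraction in the primary analysis is also a possible reading.

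**Conclusion.** The conflict is real and should be settled before analysis. The protocol's exclusion of inpatient timepoints is missing from the SAP's primary denominator, its reach to the SOC arm is unstated, the status of inpatient tests in the numerator is unstated, and the departure is undeclared.

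Under the SAP as naturally read, the consequence is misclassification of hospitalized participants and some loss of power: 0.96 to 0.80 if 20% are in hospital for 4 weeks with no test recorded, and essentially none if every inpatient week has a recorded test. Arm bias follows only from a DBS-only exclusion or from inpatient capture that differs by arm. For a DBS-only exclusion under equal adherence it ranges from 0 (all inpatient weeks tested) to about 10 points or more (none tested, 20–30% hospitalized for several weeks), against a planned difference of 25–30 points. Every figure beyond the single-participant example rests on assumed admission and capture rates.

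**What to change.** State one rule for both arms in Protocol 11.1.1 and in SAP 3.3.2, 3.3.4, 3.3.5 and Appendix 4, with numerator and denominator matched:

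- Primary: remove admission-to-discharge days from the expected-test intervals, and drop tests done during those days from the numerator, in DBS and SOC alike. Add a hospital term and a worked example to Appendix 4, including how the count resumes after hospital discharge.
- Sensitivity: keep inpatient weeks and inpatient tests in both arms.
- Make clear that the DBS-only subtraction in 3.3.2 does not enter the primary or secondary adherence analyses.
- Record the change in SAP section 17.

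The cost is SAP text and a small amount of programming. Hospitalizations are collected for all randomized subjects (Protocol 7.5 and 7.6), and SAP Table 29 lists admission and discharge days. The one limit is the University of Minnesota, where the recommended schedule was not recorded (SAP 3.3.4), so the removal cannot be applied directly. The SAP should state how that site is handled and use the existing analysis that excludes it as the check.
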